3. **(Primary)** The program will improve the health and development of firstborn children who will exhibit: a) superior cognitive, language, and academic functioning, and executive cognitive functioning (ECF); b) less depression and anxiety; c) fewer failed conduct grades and school disciplinary actions, d) less violent behavior and gang membership, and fewer arrests, juvenile detentions, and convictions – especially for crimes involving interpersonal violence.

4. **(Primary)** The program will reduce youth risk for HIV infection, including a) use of substances and SUDs; b) risky sexual behaviors; c) sexually transmitted infections (STIs) and d) pregnancies.
5. **(Primary)** Program effects on youth will be more pronounced for a) males, b) those born to low-resource mothers, and c) those living in the most disadvantaged neighborhoods at registration.

Revised Child Outcome Hypotheses

3. **(Primary)** The program will improve the health and development of firstborn children who will exhibit: a) superior cognitive, language, and academic functioning; b) less depression and anxiety; d) less gang membership, and fewer arrests, convictions, and self-reported antisocial behavior - especially for crimes involving interpersonal violence.
4. **(Primary)** The program will reduce youth risk for HIV infection, pregnancies, births, use of substances, and SUDs.
5. **(Secondary)** The program will improve firstborn children's executive cognitive functioning (ECF); and rates of high school graduation.
6. **(Primary)** Program effects on cognitive, language, and academic functioning, and executive cognitive functioning will be more pronounced among those born to low-resource mothers and on arrests and convictions among females.

Maternal and Child Outcomes (Not Revised)

7. **(Secondary)** Program effects on mothers and youth, in preliminary analyses, will be more pronounced for those with genetic vulnerabilities:
 - a. Effects on youth depression and anxiety will be greater for those with low-activity genotypes (S/S, L_G/L_G, S/L_G) of the serotonin transporter gene (*SLC6A4*) promoter polymorphism, 5-HTTLPR, compared to those with high-activity genotypes (L_A/L_A); effects on these outcomes will be of intermediate magnitude for those with intermediate activity-level genotypes (S/L_A, L_A/L_G).

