The primary analyses made use of general linear model methods and their extensions. The focus was on full model specification to account for all sources of variation, and a full examination of interactions among model factors. The primary classification factors for examination in our models, as determined by our hypotheses and earlier work, include treatments (Control vs. Nurse Visited - T), maternal psychological resources (low versus high – P), and sex of child (S). Standard covariates included an index of household poverty, maternal beliefs associated with child abuse, and for child outcomes, age of the child at the 18-year interview. Genetic analyses included the gene as an additional classification factor and were interacted with treatment status only (see more information below). We employed pared-down versions of full model specification when we had infrequently occurring outcomes (e.g. convictions for interpersonal violence). In general the approach involved beginning with a fully specified model and continuing to eliminate non-significant interactions unless a specific a priori hypothesis forced the interaction term(s) into the model.

Continuous variables were run with a general linear model; dichotomous variables with binomial error distributions; low frequency count variables with negative binomial distributions. For outcomes measured over the life course, the above models were extended to mixed or generalized mixed models to account for correlated data (random effects for time with unstructured variance terms). Subsequent children analyses were also run with mixed or generalized mixed models to account for correlation within the same family. We were interested in the treatment effects for subsequent children alone, as opposed to an overall family effect that would include the first born children.

We employed Cox proportional hazard models²³² for outcomes with a survival component. We present in the tables adjusted hazard rates at age 18 since the vast majority of the sample was interviewed after their 18th birthday but rapidly drops off after this date. The methods used for the mortality analyses can be found elsewhere.¹¹

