Inclusion of Gene Activity Classification Factors. Some of our models included classification factors for functional classifications (activity variants) of the polymorphisms hypothesized to moderate program impact in this trial (5-HTTLPR, MAOA-LPR, and COMT Val158Met); we were not interested in genotypes per se, but rather functional classes that group genotypes by activity level (low – L, high - H or intermediate - I). In the case of 5-HTTLPR, L_G and S alleles are both low-activity variants that lead to low expression; from the analysis standpoint, the low-activity genotypes (L_G/L_G, S/S, and L_G/S) were grouped into the low-activity class; the high activity genotypes (L_A/L_A) into a high-activity class; and the remaining genotypes (L_A/L_G and L_A/S) grouped into an intermediate class. We used a similar approach with MAOA-LPR and COMT Val158Met. In the case of the X-linked MAOA-LPR, we grouped males into high and low expression allele groups and excluded females from analyses. In the COMT Val158Met analyses, we excluded non-African ancestry participants.

Tests of Hypotheses

Maternal Outcome Hypotheses

Hypothesis 1 (primary): The program will continue to improve maternal life-course reflected in total costs for welfare (SNAP, AFDC/TANF, and Medicaid), especially for mothers with high psychological resources. We tested Hypothesis 1 by examining the primary maternal life-course outcome (public expenditures for SNAP, AFDC/TANF and Medicaid) in our primary model, estimating public expenditures for these benefits over time, which included a factor for T and P, the interaction between these classification factors (T x P), and a set of covariates. For the public benefit expenditure outcome, we analyzed the data in mixed models that included, in addition to the core model terms, women as levels of a random factor, a fixed repeated measures classification factor for time (first-born child age) of assessment, and all interactions of time with the other fixed classification factors. We examined the treatment–control difference summing across levels of maternal psychological resources, and conducted planned contrasts for women in the high-resource group.

Hypothesis 2 (secondary). The program will reduce maternal SUDs and depression. We examined SUDs and depression by examining planned contrasts within the classification structure specified for Hypothesis 1, using generalized linear models, logistic for depression and SUD.

Child Outcome Hypotheses

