Hypothesis 6 (primary): Program effects on cognitive, language, and academic functioning, and executive cognitive functioning will be more pronounced a) among those born to low-resource mothers and b) on arrests and convictions among females.. We will test the hypothesized conditional effects in the core model (TxPxS with covariates). Planned contrasts for children will focus the treatment contrast on children born to low-resource mothers for cognitive, language, and academic functioning, and executive cognitive functioning outcomes. Planned contrasts for arrest and conviction will focus the treatment contrast on females.

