Hypothesis 7 (secondary): Program effects on mothers and children will be more pronounced for those with genetic vulnerabilities: a) Effects on youth depression and anxiety will be greater for those with the low-activity 5-HTTLPR genotypes (S/S, L_G/L_G, S/L_G) compared to those with the high-activity genotypes (L_A/L_A); effects on these outcomes will be of intermediate magnitude for those with intermediate activity genotypes (S/L_A). We will test this hypothesis by adding a 3-level 5-HTT genetic vulnerability factor to the statistical model and examining treatment–control differences within levels of genetic risk. b) Effects on youth violent antisocial behavior, SUDS, and risky sexual behavior, including STIs and pregnancies, will be more pronounced among males with the MAOA-LPR low-activity alleles and among both males and females with the Val/Val (H/H) COMT genotype. We will repeat the analysis of child outcomes, substituting first a factor that classifies the sample into groups of MAOA alleles that confer high versus low activity, focusing the treatment contrast on males within the low-MAOA category; we will repeat this analysis for both males and females, substituting the COMT genotype as the genetic vulnerability factor, focusing the treatment contrast on the high-activity subgroup (Val/Val). c) Effects on maternal SUDs will be concentrated among those mothers with the Val/Val COMT genotype. In testing this hypothesis, we again will add the COMT genotype (H/H, H/L, LL) to our standard model and repeat the analysis of maternal SUDs, focusing on our planned treatment contrast on the H/H subgroup. d) Effects on child outcomes will be more pronounced among children born to mothers with either: 1) the low-activity 5-HTTLPR genotypes; or 2) 2 copies of the high-activity COMT Val158 alleles (COMT-H). In testing this hypothesis, we again will add the 5-HTTLPR genetic risk factor to our standard models and repeat the analysis of child outcomes, with planned contrasts focusing on treatment–control differences within the low-activity 5-HTTLPR subgroup defined by mothers’ having either high- low- or intermediate activity classifications. Given limited statistical power to examine treatment contrasts within any one of these subgroups alone, we also will create a maternal genetic risk factor based upon whether mothers possess any one of these risk genotypes and then re-run the analysis of treatment-control differences focusing on planned comparisons within the high genetic risk factor defined by mothers possessing either one of these 2 risk genotypes.

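### Hypothesis 6 claims effects are larger in one subgroup, but the contrasts it names test only whether the effect inside that subgroup is non-zero

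*Protocol*

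**What the plan says.** Under Revised Child Outcome Hypotheses, no. 6 is labelled primary and is comparative: "Program effects on cognitive, language, and academic functioning, and executive cognitive functioning will be more pronounced among those born to low-resource mothers", with a parallel claim for arrests and convictions among females.

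The analysis is given under Tests of Hypotheses, Hypothesis 6. The conditional effects are to be tested in the core model of treatment (T), maternal psychological resources (P) and child sex (S). Two contrasts are then named: "Planned contrasts for children will focus the treatment contrast on children born to low-resource mothers" for the cognitive, language, academic and executive outcomes, and "Planned contrasts for arrest and conviction will focus the treatment contrast on females".

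Other hypotheses follow the same pattern:

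- **Hypothesis 1 (primary).** T×P is in the model and a whole-sample contrast is planned. For the clause about high-resource mothers, the analysts "conducted planned contrasts for women in the high-resource group".
- **Hypothesis 7b to 7d (secondary).** The contrast sits inside the group of interest, for example "focusing the treatment contrast on males within the low-MAOA category", Val/Val carriers, or mothers with risk genotypes.
- **Hypothesis 7a (secondary).** This differs, since it involves "examining treatment–control differences within levels of genetic risk" across all three 5-HTTLPR classes, but it names no comparison between the classes.

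Statistical Models and Methods of Analysis promises a full look at interactions and describes "continuing to eliminate non-significant interactions unless a specific a priori hypothesis forced the interaction term(s) into the model".

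**The concern.** A claim that an effect is larger in one stratum is a claim about the difference between two effects. A treatment contrast confined to one stratum says nothing about that difference, because it never uses the other stratum. An effect of the same size in both groups can make the low-resource contrast significant and so be read as support for moderation.

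The rule on interactions does not close the gap. It governs which terms stay in the model, and a priori terms stay whatever their p-value; it does not say what result permits the conclusion.

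At stake is a primary statement about which families the program helps most. The whole-sample tests (Hypotheses 3 to 5 and the first part of Hypothesis 1) and the subgroup estimates themselves are not affected.

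**Working it through.** The protocol gives no alpha, power or detectable difference for this hypothesis, so there is no figure of its own to reproduce.

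**Inputs**

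- Youth assessed at 18 years: 435 control, 194 nurse-visited (Table 2).
- Low-resource share: not given. Assumed 50%, with 40% and 60% as the range.
- Two-sided alpha 0.05 (assumed), outcomes in SD units, no covariate adjustment.
- Effect sizes: the whole-sample cognitive and achievement values in Table 1, which are 0.04, 0.12, 0.17 and 0.18.

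**Step 1: standard errors**

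SE(low-resource contrast) = √(1/217.5 + 1/97) = 0.122 SD.

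SE(T×P contrast) = √2 × 0.122 = 0.173 SD.

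**Step 2: chance that the named contrast is significant and favourable when both strata have the same effect d**

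P = Φ(d/SE − 1.96).

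| d | 50% share (SE 0.122) | T×P contrast |
|---|---|---|
| 0.04 | 0.051 | 0.025 |
| 0.12 | 0.164 | 0.025 |
| 0.17 | 0.285 | 0.025 |
| 0.18 | 0.314 | 0.025 |

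From d = 0.04 to d = 0.18 the probability runs from 0.048 to 0.261 at a 40% share (SE 0.137), and from 0.055 to 0.365 at a 60% share (SE 0.111). A simulation of 20,000 trials at d = 0.20 and a 50% share gave 0.37 for the low-resource contrast (two-sided), matching the formula, and 0.051 for the two-sided interaction test.

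**Step 3: what Table 1 implies about moderation**

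Table 1 gives whole-sample and low-resource effects only. With equal halves, the implied high-resource effect is 2 × whole − low. The age-18 numbers stand in for those at earlier ages, so the SE of the difference is about 0.173.

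| Outcome | Whole | Low | Implied high | Low − high | z |
|---|---|---|---|---|---|
| KABC, age 6 | 0.18 | 0.25 | 0.11 | 0.14 | 0.8 |
| PPVT, age 6 | 0.17 | 0.21 | 0.13 | 0.08 | 0.5 |
| Achievement, age 6 | 0.04 | 0.19 | −0.11 | 0.30 | 1.7 |
| Achievement, age 12 | 0.12 | 0.29 | −0.05 | 0.34 | 2.0 |

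A check that does not use the age-18 numbers takes the SE from the whole-sample p-value and doubles it for the interaction. For KABC, the mean differences are 2.10 (whole) and 2.85 (low). The implied high-resource difference is 2 × 2.10 − 2.85 = 1.35, so low minus high is 1.50 and p is about 0.44. The same method gives about 0.65 for PPVT, 0.057 for age-6 achievement and 0.037 for age-12 achievement.

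KABC shows the problem most clearly: its low-resource p is .03, yet the implied difference between strata is well within noise.

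Table 1 outcomes outside Hypothesis 6 are also mixed. In the claimed direction, the implied differences are 0.30 for dysregulated aggression (z 1.7), 0.36 for incoherent stories (2.1), 0.12 for the Bavolek score (0.7) and 0.20 for NCAST (1.2, using the absolute effect size because the means favour the nurse group). HOME runs the other way: 0.21 − 0.27 = −0.06 (0.3).

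**Step 4: power of the correct test**

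The difference detectable with 80% power is 2.80 × 0.173 = 0.48 SD, or 0.49 with a 40/60 split.

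The arrest and conviction claim, Hypothesis 1 and Hypothesis 7 cannot be quantified, because the document gives no age-18 rates, costs or genotype-specific effects.

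**The case against.** The best reply is that the interaction is already there. Hypothesis 6 opens with "We will test the hypothesized conditional effects in the core model (TxPxS with covariates", the Hypothesis 1 text lists T×P explicitly, and genetic factors are interacted with treatment. No sentence says that a significant within-subgroup contrast is enough. On this reading only a decision rule is missing, and that could sit in an SAP.

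It is true that the terms are fitted. But the sentences that follow in Hypothesis 6 name the contrasts, and both are within a stratum, so this is not silence left for an SAP to fill. The protocol does state a decision criterion where it wants one, as Hypothesis 8 does for mediation. It also already reasons from within-subgroup results: mediation models are chosen from outcomes that differ in the low-resource group, and the power caveat in Hypothesis 7 concerns contrasts within subgroups.

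Four narrower points have some force:

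- The probabilities in Step 2 treat every favourable significant low-resource result as a moderation claim. If a non-significant high-resource result were also required, the figures would be 0.164 × 0.836 = 14% at 0.12 and 0.314 × 0.686 = 22% at 0.18, still far above 2.5%.
- All four Table 1 outcomes of the Hypothesis 6 type run in the predicted direction, and so do the injury rates. Moderation may well be real for some outcomes; the point is that it must be tested directly.
- Hypothesis 1 is fitted over time, so a T×P contrast there must say how time is handled.
- Interaction power is low: about 50% at the age-12 achievement difference of 0.34.

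**Conclusion.** The concern holds. For a primary comparative hypothesis, the protocol names contrasts that answer a different question, and nothing in the document makes T×P, T×S or treatment-by-gene the basis for the claim. With equal true effects of 0.04 to 0.18 SD in both strata, the named contrast is favourable and significant 5% to 31% of the time, against 2.5% for the interaction. The upper figure is 26% at a 40% low-resource share and 36% at 60%.

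These numbers rest on the assumed share, two-sided 5% tests and continuous unadjusted outcomes, and apply to the low-resource part of Hypothesis 6 only. For the female contrast, the high-resource clause of Hypothesis 1 and Hypotheses 7b to 7d, the flaw is the same in form but unquantified. Hypothesis 7a lacks only the comparison between classes. This should be fixed before any moderation conclusion is drawn.

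**What to change.** State that a claim of a more pronounced effect is judged by the interaction contrast:

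- **Hypothesis 6, resources, and the high-resource clause of Hypothesis 1:** T×P, that is (T4 − T2) in one resource stratum minus (T4 − T2) in the other. For Hypothesis 1, state that the contrast is taken on the 18-year total.
- **Hypothesis 6, arrests and convictions:** T×S. For negative binomial counts this is a ratio of rate ratios, and the scale should be stated.
- **Hypothesis 7:** treatment-by-gene, comparing the low, intermediate and high classes for 7a.

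Report the treatment effect in both strata (all classes for genes) with confidence intervals, and present within-subgroup contrasts as conditional estimates only. If the team's real interest is the effect within the named subgroup, the alternative is to reword the hypothesis that way and drop the comparative claim.

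The cost in work is small, since the interaction terms are already in the models and no new data are needed. The real cost is power: the roughly 0.48 SD needed for 80% power exceeds every difference implied by the effect sizes worked through above (largest 0.36). The protocol should say so, and an inconclusive interaction should be reported as inconclusive.
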